7.3 Key Secondary Efficacy Analysis

The key secondary efficacy analyses will be based on the ITT population. The primary efficacy analyses will be repeated for responder wounds that meet any of the following conditions:

- Healed on Week 8 and Week 10, or
- Healed on Week 10 and Week 12.

Only wounds that are healed for at least two (2) consecutive weeks are counted as positive responses. The key secondary endpoint response data will be summarized descriptively by the wound treatment.

The McNemar testing procedure used for the primary endpoint will be repeated for this key secondary endpoint. A multiple imputation approach (details see section [7.1.6](#)) assuming MAR will be used to impute missing endpoint data. If the primary endpoint is statistically significant at a type I rate of 0.05, the same full type I rate of 0.05 will be passed on to evaluate the key secondary endpoint.

7.3.1 Sensitivity and Supplementary Analyses of the Key Secondary Efficacy Endpoint

Sensitivity analyses of the key secondary endpoint include:

- The analysis described in Section 7.3 for the key secondary efficacy endpoint will be repeated for the PP and mITT populations.
- The key secondary efficacy analysis performed in Section 7.3 for the key secondary efficacy endpoint will be repeated with observed data without any imputations for missing values (i.e., if a subject is missing either a B-VEC or placebo outcome, the subject will be excluded from the analysis).

Supplementary Analysis:

- Common treatment risk difference will be obtained from conditional logistic regression with covariates age and gender and stratified by subject (matched pair) and multiple imputation approach described in section 7.1.6 assuming MAR.

7.4 Secondary Efficacy Analyses

The following secondary endpoints will be analyzed using Analysis of Covariance (ANCOVA) with treatment as the fixed effect, and the baseline value as the covariate. The analyses will be conducted in the ITT population for the matched Primary Wound Pair only.

1. The mean change in pain severity VAS score per wound site associated with wound dressing changes at Week 22 for each B-VEC-treated wound versus placebo-treated wound for ages 6 and above. For ages below 6 years, the FLACC-R scale scores will be used instead of VAS scores and will be summarized descriptively.
2. The analysis will be repeated for Week 24 and for Week 26.

All results will be summarized by treatment and timepoints. A listing of these results will also be presented for all the subjects in the ITT population.

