## Schedule of Events

**Table 1. Visit Assessments and Procedures**

Study Day	Randomized-Double Blinded Placebo-Controlled Treatment Period								Safety Follow-up/ET
	Screening 	Week 1	Week 2 -21	Week 22	Week 23	Week 24	Week 25	Week 26	30 days after last dose
Daily Visit Window	-60 to 0	na	± 3 days						± 4 days
Visit	Screening	1	2-21	22	23	24	25	26	SFU
Obtain Consent / Assent	X	X 							
Inclusion/Exclusion Criteria		X							
Demographics	X	X 							
Medical History	X	X 							
Genetic Testing	X 								
Wound Selection		X							
Wound randomization 		X							
Pain Assessment- Wound Pair 		X		X		X		X	
Quality of Life Questionnaire (EQ-5D) 		X						X	
Skindex Questionnaire 		X						X	
Imaging 		X	X	X	X	X	X	X	X
Assessment of Wound Closure 		X	X	X	X	X	X	X	
Swabs for Viral Shedding/Infectivity 		X	X	X	X	X	X	X	
Swabs for Viral Shedding on Dressing Returned 			X						

 If genetic testing is required, this test may occur up to 60 days prior to the other screening procedures, following subject consent/assent. Genetic testing may take 6-8 weeks to obtain results.

 Informed consent/assent, demographics, medical/ procedural history, urine (if male) and blood specimens will not be re-collected, if collected at a Screening visit.

 The matched primary wound pair will be randomized.

 Pain questionnaires are to be completed during the dressing change of the individual matched wounds. If subject is 6 years of age or older, they will be asked to complete the VAS questionnaire for matched wounds during the dressing change. If younger than 6 years of age, their parent/caregiver will be administered the FLACC-R questionnaire for the matched wounds during the dressing change (Refer to section 6.2.2).

 Both the Quality of Life (EQ-5D) and Skindex Questionnaires will be administered to subjects 12 years of age and older at the time of consent. Questionnaires may be administered for the subject to complete after the visit and bring back at the next scheduled visit.

 Images will be collected on both closed and open wounds. Image in the same order and orientation at each visit prior to IP application.

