## **3 Selection of Subjects**

This study is planned to enroll approximately 24 participants with DEB, aged 6 months or older at the time of Informed Consent.

The study team cooperates with national and international networks of families, researchers, and physicians who care for children and adults with EB, and it is planned to use these groups to recruit participants for this study. In addition, an email and clinical study information may be posted to national communities (EB foundations, e.g., Dystrophic Epidermolysis Bullosa Research Association of America, site-specific EB websites) regarding recruiting for this study.

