## 8.7 Efficacy Analyses

### 8.7.1 General Approach

The study has a complete randomized-block design in which each subject serves as a block to receive all of the treatment conditions. In this study, each subject provides at least one pair of target wounds with one wound from each pair being treated with B-VEC and the other wound from each pair with placebo in the primary target wound pair. Efficacy measurements are taken multiple times (or repeatedly) over the on-treatment period from each subject.

All data will be presented using summary statistics or frequency tables, as appropriate, and will be analyzed for superiority comparisons between B-VEC and placebo treatments. The description of the sample will be done using summary statistics (n, mean, standard deviation, median, and maximum/minimum) for continuous data and using frequency statistics (counts and percentages) for categorical data. Hypothesis

testing, unless otherwise indicated, will be performed at the 5% significance level (1-sided). All P-values will be rounded to four decimal places; P-values less than 0.0001 will be presented as '<0.0001' in all tables. Unless specifically stated, all confidence intervals will be two-sided with 95% coverage.

Efficacy measures collected pre-dosing at Screening or Visit 1 (Week 1) will be considered as the baseline measurement in this study.

The Sponsor, or their designee, will analyze the data using SAS® Statistical Analysis System Version 9.1.3 or higher. Detailed descriptions of the statistical analysis methods, data conventions, and sensitivity analysis, as well as handling of missing data for both efficacy and safety measures will be described in detail in the Statistical Analysis Plan (SAP).

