#### **8.7.4 Analysis of Secondary Efficacy Endpoint**

The following secondary endpoint will be analyzed using the Analysis of Covariance (ANCOVA) with treatment as the fixed effect and the baseline value as the covariate by the time points.

The mean change from baseline in pain severity VAS score per wound site associated with wound dressing changes at Weeks 22, 24 and 26 for each treated versus placebo for ages 6 and above on the primary wound pair. For ages below 6 years, the FLACC-R scale scores will be used instead of VAS scores.

The ITT population will be used for this primary efficacy analysis. The ITT and PP populations may also be used as part of the sensitivity analyses.

The secondary endpoint results will be summarized by treatment and timepoints for all the subjects in the ITT population. A listing of these results will also be presented for all the subjects in the ITT population.

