7.2.1 Sensitivity and Supplementary Analyses of the Primary Efficacy Endpoint

Sensitivity analyses of the primary endpoint include:

- The primary analysis described in Section [7.2](#) for the primary efficacy endpoint will be repeated for the PP and mITT populations.
- The primary analysis described in Section [7.2](#) for the primary efficacy endpoint will be repeated with observed data without any imputations for missing values (i.e., if a subject is missing either a B-VEC or placebo outcome, the subject will be excluded from the analysis).

Supplementary Analysis:

- Common treatment risk difference will be obtained from conditional logistic regression with covariates age and gender and stratified by subject (matched pair) and multiple imputation approach described in section [7.1.6](#) assuming MAR.

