7.4.1 Sensitivity Analyses of the Secondary Efficacy Endpoints

Sensitivity analyses of the secondary endpoints include:

- The analyses described in Section 7.4 for the secondary efficacy endpoints will be repeated for the PP and mITT populations.

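### The pain (VAS) ANCOVA has no subject term for the wound pair; with the likely positive within-subject correlation its standard error is too large and the precision of the paired design is lost

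*SAP*

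**What the plan says.** SAP 7.4 specifies the pain analysis as "Analysis of Covariance (ANCOVA) with treatment as the fixed effect, and the baseline value as the covariate". It is run in the ITT population on the Primary Wound Pair, once for each of Weeks 22, 24 and 26, and compares B-VEC-treated with placebo-treated wounds. Protocol 8.7.4 lists the same terms: "Analysis of Covariance (ANCOVA) with treatment as the fixed effect and the baseline value as the covariate by the time points". The synopsis agrees.

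The scores are paired. Footnote 4 to Table 1 of the protocol's Schedule of Events states: "Pain questionnaires are to be completed during the dressing change of the individual matched wounds". Under Protocol 6.2.2.2, subjects aged 6 or above complete the VAS themselves, so one person rates both wounds at one visit.

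The protocol describes the design in 8.7.1 as a "complete randomized-block design in which each subject serves as a block to receive all of the treatment conditions". The healing analyses follow that design. SAP 7.2 and 7.3 use McNemar's test on pairs, and the supplementary analysis in SAP 7.2.1 is a "conditional logistic regression with covariates age and gender and stratified by subject (matched pair"), repeated in 7.3.1. For pain, the only sensitivity analysis, in SAP 7.4.1, is: "The analyses described in Section 7.4 for the secondary efficacy endpoints will be repeated for the PP and mITT populations".

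Two statements bear on the number of pairs. Protocol Section 3 plans for "approximately 24 participants with DEB, aged 6 months or older at the time of Informed Consent". SAP 7.4 limits the pain model to the older subjects: "For ages below 6 years, the FLACC-R scale scores will be used instead of VAS scores and will be summarized descriptively".

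**The concern.** No section names a subject effect, a within-subject covariance or an analysis of within-pair differences for pain. A programmer who follows SAP 7.4 would fit treatment and baseline to 2n wound scores as if they came from 2n independent units.

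Two scores given by the same person at the same visit are likely to share a subject component that each wound's own baseline does not fully remove. Ignoring it does not bias the treatment estimate, because each subject supplies one wound per treatment. It does make the reported standard error wrong. With positive correlation the confidence interval is too wide and the test rejects less often than its nominal level, so a real pain effect is more likely to be missed. With negative correlation the test would reject too often.

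What is at stake is the pain endpoint alone.

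**Working it through.** **The plan's own figure.** SAP 3.1.3 gives 24 pairs for McNemar's test at 75% vs 25% response, independence, 90% power and two-sided 5%. The discordant probabilities are 0.75 × 0.75 = 0.5625 and 0.25 × 0.25 = 0.0625. Full enumeration of the exact binomial version gives 88.8% power at 23 pairs and 90.5% at 24, so 24 is reproduced. That calculation concerns healing only. No SD, effect size, correlation or power is stated for pain, so those below are assumptions.

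**Formula.** Let n be the number of pairs, σ the residual SD after baseline adjustment, and ρ the residual correlation between a subject's two wounds. Leaving aside estimation of the baseline slope:

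- true SE of the treatment difference = σ√(2(1 − ρ)/n)
- SE reported by the model as written ≈ σ√(2/n)
- ratio, reported to true ≈ 1/√(1 − ρ)

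With n = 24 and σ = 1, the reported SE is √(2/24) = 0.289. The true SE is √(1.6/24) = 0.258 at ρ = 0.2 (ratio 1.12) and √(1/24) = 0.204 at ρ = 0.5 (ratio 1.41).

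**Simulation.** There were 20,000 trials per setting. Baseline SD was 1 with between-wound correlation 0.6. Change = −0.5 × baseline + δ × treatment + residual, with residual SD 1 and correlation ρ. As written: least squares on 2n rows with treatment and baseline (2n − 3 df). Paired: regression of the within-subject difference in change on the difference in baseline (n − 2 df). Results for 24 pairs, with power at δ = 0.6:

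| ρ | Reported SE, as written | Actual SE, as written | Type I error, as written | Type I error, paired | Power, as written | Power, paired |
|---|---|---|---|---|---|---|
| −0.3 | 0.289 | 0.332 | 8.5% | 5.1% | 52.5% | 40.3% |
| 0 | 0.288 | 0.289 | 4.9% | 4.8% | 52.9% | 49.9% |
| 0.1 | 0.288 | 0.275 | 3.9% | 5.0% | 52.0% | 53.0% |
| 0.2 | 0.288 | 0.260 | 3.0% | 5.0% | 53.3% | 58.7% |
| 0.3 | 0.287 | 0.243 | 2.1% | 5.1% | 53.5% | 64.3% |
| 0.5 | 0.287 | 0.206 | 0.7% | 5.0% | 54.1% | 78.3% |
| 0.7 | 0.286 | 0.162 | 0.1% | 5.1% | 54.8% | 94.0% |

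The reported SE is too large by 0.288/0.260 − 1 = 11% at ρ = 0.2, 0.287/0.243 − 1 = 18% at 0.3, and 0.287/0.206 − 1 = 39% at 0.5. These agree with the formula apart from the cost of estimating the slope. The mean as-written estimate for a true 0.6 was between 0.597 and 0.605, so there is no bias.

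As-written power stays near 54% for a simple reason. The model rejects when the estimate exceeds about 2.01 × 0.287 = 0.58, just below the assumed 0.6, so power sits just above one half however tight the true distribution is.

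**Sensitivity to the assumptions** (as written vs paired power):

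- 24 pairs, ρ = 0.5: 20% vs 45% for an effect of 0.4 SD, and 85% vs 95% for 0.8 SD.
- 20 pairs, ρ = 0.5, 0.6 SD: 44% vs 70%.
- 18 pairs, 0.6 SD: 41% vs 38% at ρ = 0, 41% vs 45% at 0.2, and 39% vs 64% at 0.5.

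**The case against.** The strongest reply is that an omission is not an exclusion. Protocol 8.7.1 sets the general approach for all efficacy analyses and makes the subject a block. SAP 7.4 confines the analysis to the matched pair, and naming treatment as the fixed effect does not forbid a random subject effect. On that reading the model is under-specified rather than wrong. This stands only in part. The protocol leaves detailed methods to the SAP, and the SAP names the pairing where it uses it for healing but not for pain. If a subject term is intended, it still has to be written down.

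Second, the harm is limited. The estimate is unbiased, and for the likely sign of the correlation the error is conservative and cannot create a false claim. Pain also lies outside the alpha step from primary to key secondary endpoint in SAP 7.3, so its three weekly p-values are nominal. All of this stands, and it keeps the point well below a threat to the trial's main conclusion. It does not make the interval correct.

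Third, the size is assumed throughout. The relevant correlation is what remains after adjustment for each wound's baseline, and the documents do not inform it. The VAS is marked at 1 cm ticks from 0 to 10, and ties or floor effects were not simulated. The figure of 24 is an approximate target, not a ceiling, and any child under 6 lowers the number of pairs in the model. These points stand: the power figures are illustrations. The omission and the direction of the error do not depend on them.

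**Conclusion.** The concern holds. As listed in both documents, the pain model ignores the pairing that the design creates, and nothing in the sensitivity analyses restores it. Its standard error is valid only at zero residual correlation.

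The size depends on that unknown correlation. At 0.2 or below the loss is small, about 6 power points or less. At 0.5, with 24 pairs and an effect of 0.6 SD, the standard error is about 39% too large and power falls from 78% to 54%. A negative correlation, which is unlikely here, would inflate type I error: 7.5% at −0.2 in the same simulation.

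The wording should be corrected before the pain data are analysed.

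**What to change.** In SAP 7.4 and Protocol 8.7.4 (and the synopsis), keep the baseline-adjusted ANCOVA at each of Weeks 22, 24 and 26 and add the subject as a block. Two forms are suitable:

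- a within-subject compound-symmetry covariance for the two wounds; or
- a regression of the B-VEC minus placebo difference in change on the same difference in baseline, with the intercept as the treatment effect. This is equivalent to a fixed subject block.

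If a random subject effect is preferred, its variance should not be constrained to be non-negative. In 1,500 simulated trials at correlation −0.2 with 24 pairs, the constrained version had 8.0% type I error, against 5.7% for unconstrained compound symmetry. This is a safeguard, secondary to naming the block at all. SAP 7.1.2, which says that efficacy analyses use no covariate adjustment, should be reconciled with the baseline covariate in 7.4 in the same edit.

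The cost is wording only, with no new data. If the correlation is in fact zero, the paired analysis loses about 3 to 4 power points at 24 pairs. The difference version also drops any subject with one wound's score missing. Compound symmetry avoids that but assumes equal variance in the two wounds.

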6.3 Treatment Compliance and Exposure

Exposure summary by treatment group (primary wounds only) will be presented for the Safety, mITT, and PP populations. The distribution of subjects by the total number of weeks on therapy (0 through 26) will be presented. For the Safety population, the summary of exposure will be based on the actual treatment received.

Treatment compliance is defined as the number of wound treatment doses (active and placebo) actually received divided by the number of doses expected ($\times 100$) over the time period defined by the first and last treatment dose dates. Descriptive statistics for treatment compliance and the number and percentage of

subjects at least 90% compliant will be presented by treatment group (primary wounds only) for the Safety, mITT, and PP populations.

7 Efficacy Analyses

All data will be presented using summary statistics or frequency tables, as appropriate, and will be analyzed for superiority comparisons between B-VEC and placebo treatments. The description of the sample will be done using summary statistics (n, mean, standard deviation, median, and maximum/minimum) for continuous data and using frequency statistics (counts and percentages) for categorical data. Hypothesis testing, unless otherwise indicated, will be performed at the 5% significance level (2-sided). All P-values will be rounded to four decimal places; P-values less than 0.0001 will be presented as '<0.0001' in all tables. Unless specifically stated, all confidence intervals will be two-sided with 95% coverage.

Efficacy measures collected pre-dosing at Screening or Visit 1 (Week 1) will be considered as the baseline measurement in this study.

The Sponsor, or their designee, will analyze the data using SAS® Statistical Analysis System Version 9.4 or higher.

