7.1.4 Multiple Comparisons/Multiplicity

The primary efficacy endpoint is a single responder outcome during weeks 24 through 26 that will be compared between two treatment groups. Therefore, the primary analysis will not be adjusted for multiple comparisons.

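### The secondary pain endpoint is tested at Weeks 22, 24 and 26, each at two-sided 5%, with no deciding week, order, adjustment or link to the SAP's testing sequence

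*SAP*

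**What the plan says.** Pain at dressing change is the Secondary Endpoint in both documents (Protocol 2.2.4, SAP 2.2.4). The protocol synopsis lists it apart from the exploratory endpoints.

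- **Tests.** SAP 7.4 specifies "Analysis of Covariance (ANCOVA) with treatment as the fixed effect, and the baseline value as the covariate", for the VAS change "associated with wound dressing changes at Week 22 for each B-VEC-treated wound versus placebo-treated wound for ages 6 and above". It then adds "The analysis will be repeated for Week 24 and for Week 26". Protocol 8.7.4 uses the same kind of model, "with treatment as the fixed effect and the baseline value as the covariate by the time points".
- **Level.** The opening of SAP section 7 says "Hypothesis testing, unless otherwise indicated, will be performed at the 5% significance level (2-sided"). Nothing in SAP 7.4 indicates otherwise. The protocol's default, in 8.7.1, differs: "testing, unless otherwise indicated, will be performed at the 5% significance level (1-sided").
- **Sequence.** SAP 7.3 provides that, once the primary is significant at 0.05, "the same full type I rate of 0.05 will be passed on to evaluate the key secondary endpoint". No further step follows.
- **Multiplicity.** SAP 7.1.4 deals only with the primary endpoint: "Therefore, the primary analysis will not be adjusted for multiple comparisons".
- **Descriptive label.** SAP 7.4 makes the FLACC-R scores (under 6 years) descriptive. It does not say this of the VAS scores.

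**The concern.** A named secondary endpoint has three inferential tests and no rule that turns them into one conclusion. The plan does not say which week decides, whether one significant week is enough, or whether the pain tests may be read inferentially when the primary or key secondary has failed.

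The healing conclusions are not at risk, because the primary and key secondary are properly sequenced. What is at stake is a pain claim. A report could present the most favourable of three weeks as a positive secondary result, and nothing written in advance would stop it. With about 24 subjects, fewer of them aged 6 or above, the three weeks could well fall on different sides of 0.05.

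**Working it through.** **Plan's own figure.** The documents give no error rate for pain, so there is none to reproduce. Their one design calculation, 24 pairs for the primary McNemar test, is confirmed by exact enumeration (power 90.5% at 24 pairs, 88.8% at 23). It has no bearing on pain.

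**Inputs.** Three tests (SAP 7.4), each at two-sided 0.05 (SAP section 7). Assumed, because the documents are silent: one significant week counts as success; each test is correctly sized; the weekly test statistics have a common correlation ρ.

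**Step 1. Correctly sized tests, no pain effect at any week.** At ρ = 0:

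- any significant week: 1 − 0.95³ = 1 − 0.8574 = 14.3%
- any significant week favouring B-VEC: 1 − 0.975³ = 1 − 0.9269 = 7.3%, against 2.5% for one test

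For ρ > 0, three correlated normal statistics were simulated (4 million draws):

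| ρ (assumed) | Any week, two-sided 5% | Favouring B-VEC only | Any week, protocol's one-sided 5% | Any week, Bonferroni (0.05/3) |
|---|---|---|---|---|
| 0 | 14.3% | 7.3% | 14.3% | 4.9% |
| 0.3 | 13.6% | 6.8% | 13.0% | 4.8% |
| 0.5 | 12.6% | 6.3% | 11.9% | 4.5% |
| 0.7 | 10.9% | 5.5% | 10.3% | 3.9% |
| 0.9 | 8.4% | 4.2% | 8.0% | 3.0% |

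Under the protocol's one-sided default, every false positive favours B-VEC, so that column compares with 5% for a single test.

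**Step 2. The ANCOVA as written.** The model has treatment and baseline but no subject or pair term. If a subject's two wounds have correlation r, the true variance of the treatment difference is (1 − r) times the variance that the model assumes. Ignoring baseline and small-sample effects, the per-week rejection rate is 2Φ(−1.96/√(1 − r)):

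- r = 0.3: 1.96/0.837 = 2.34, giving 1.9%
- r = 0.5: 1.96/0.707 = 2.77, giving 0.6%

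Simulation of the full model (18 and 24 subjects, week-to-week correlation 0.3 to 0.7, 20,000 trials per setting) gives:

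| Between-wound correlation r (assumed) | Per week, as written | Any week, as written | Any week, paired model |
|---|---|---|---|
| 0 | 5% | 12–14% | 12–14% |
| 0.3 | 2.1–2.3% | 5.5–6.2% | 12–14% |
| 0.5 | 0.8% | 2.1–2.4% | 12–14% |

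A separate run with 20 subjects and r = 0.2 gave 8.7% for any week.

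**Step 3. How often the weeks would disagree.** Suppose each week has 50% power (assumed). The chance that all three are significant is 1/8 + (3/4π)·arcsin ρ, and the chance that none is has the same value. The weeks therefore disagree with probability 1 − 2 × that value:

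- ρ = 0.5: 1 − 2 × 0.250 = 50%
- ρ = 0.7: 1 − 2 × 0.310 = 38%
- ρ = 0.9: 1 − 2 × 0.392 = 22%

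The plan has no rule for reading such a result.

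**The case against.** The best reply is that pain was never meant to be confirmatory. The documents separate the key secondary from the secondary endpoint. Formal hypotheses are written only for the primary and key secondary (Protocol 8.1 and 8.2), alpha passes only to the key secondary, and pain has no power statement. On that reading only a label is missing. The reading is reasonable, but the label does matter: SAP 7.4 says descriptive for FLACC-R and gives VAS a model-based comparison, under a section that promises superiority comparisons and two-sided 5% tests.

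A second reply also has force. With the model as written, positive correlation between matched wounds on one subject, scored by the same person, is plausible, and the rate for any week could be near or below 5%. That limits what can be said about the actual rate. It does not supply control, because the protection disappears once the model is corrected for pairing.

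Three stronger readings are tempting, and the documents do not support them:

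- A reader might take one value, such as the 12.6% at ρ = 0.5, as the trial's error rate for pain. The documents give neither a correlation nor a rule that any one week suffices, and the figure also counts results favouring placebo.
- A reader might add the sequenced healing endpoints and quote 1 − 0.95 × (1 − 0.126) = 17% for any false efficacy result. That also needs pain and healing to be independent, which is doubtful for the same wounds. Nor do the documents promise a single 5% across all efficacy endpoints.
- A reader might infer that the SAP allows a pain claim after a failed primary. It does not say so. It is silent, and nothing in it prevents such a claim.

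**Conclusion.** The point stands as a gap in the rules for a secondary endpoint: three unordered, unadjusted tests outside the testing sequence, with no criterion for success.

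Its size is conditional. With correctly sized tests and any one week sufficing, the false-positive rate is about 8% to 14% two-sided, or about 4% to 7% for results favouring B-VEC against 2.5% for one test, at assumed ρ from 0.9 to 0. With the unpaired ANCOVA as written, the two-sided rate could be anywhere from about 14% down to about 2%, depending on a between-wound correlation that the documents do not give.

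The primary and key secondary conclusions are unaffected. The change should be made before unblinding, because a pain claim could not be defended on the present text.

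**What to change.** Amend SAP 7.1.4 and 7.4 and Protocol 8.7.4 in one of two ways.

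1. **If a pain claim is wanted:** extend the existing sequence. Test VAS change only if the key secondary is significant. Use either one named week or one stated order of the three weeks, each at two-sided 0.05, stopping at the first non-significant result. Week 26, then 24, then 22 is one possible order. Week 24, which belongs to both primary response windows, could equally lead. With valid tests this holds the whole sequence at 5%. Specify a model that accounts for the wound pair, for example the within-subject difference in change with the difference in baseline as covariate, or a mixed model with a subject effect.
2. **If it is not wanted:** state that the three pain p-values are nominal and support no confirmatory claim.

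In the same edit, reconcile the one-sided default in Protocol 8.7.1 with the two-sided default in SAP section 7. Protocol 8.1 and 8.2 set two-sided 0.05 for the primary and key secondary, so the conflict falls mainly on pain.

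The cost is a few sentences, with no new data or subjects. The downside is that a nominally significant pain result cannot be claimed if an earlier step fails.
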